9 STATISTICAL CONSIDERATIONS

9.1 STATISTICAL HYPOTHESES

Specific Aim 1: To determine whether DMEK has superior post-operative best spectacle corrected visual acuity (BSCVA) compared with UT-DSAEK or DSO with a similar safety profile.

- We hypothesize that the DMEK group will have improved visual acuity compared with UT-DSAEK at all time points.*
- We hypothesize that the DMEK group will have improved visual acuity compared with DSO at all time points.*

Specific Aim 2: To determine the benefit of adjuvant rho-kinase inhibitors on endothelial cell loss in patients who received UT-DSAEK and DMEK.

- We hypothesize that endothelial cell loss will be higher after DMEK than UT-DSAEK.*
- We hypothesize that endothelial cell loss will be lessened among those receiving ripasudil, after controlling for the pre-operative ECD in DMEK and UT-DSAEK.*

Primary Endpoints:

- Best spectacle-corrected visual acuity (BSCVA) at 12 months
- Endothelial cell loss at 12 months

Secondary Endpoints:

- Specific Aim 1: BSCVA at 3, 6, and 24 months
- Specific Aim 1: Complications over the course of the entire study period, including re-bubble rate, graft rejection, primary graft failure, and need for further surgery.
- Specific Aim 2: Endothelial cell density at 3, 6, and 24 months
- National Eye Institute Visual Function Questionnaire (VFQ) post-operatively at 3 months and 12 months as compared to baseline
- Adverse events over entire study period
- Corneal haze and higher-order aberrations as measured by Pentacam at baseline and post-operatively at 3, 6, 12, 24 months
- Graft thickness as measured by optical coherence tomography and pachymetry on donor tissue pre-operatively and post-operatively at 6 and 12 months
- Cost-effectiveness analysis at 24 months
- Manifest refraction at baseline and post-operatively at 3, 6, 12, 24 months

DETECT

Version 5.0
21 March 2023

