surgeons and may not be generalizable to most corneal specialists. It was also not powered to detect differences in important secondary outcomes such as re-bubble rate, primary graft failure, change in endothelial cell densities (ECDs) or vision-related quality of life. These limitations, along with the fact that there have been one other small randomized clinical trial and one other prospective comparative case series which have not found a difference in visual acuity outcomes between DMEK and UT-DSAEK or Nanothin-DSAEK (<50µm), support the need for additional rigorous study comparing these techniques.^{8,9} *A larger, multi-center, multi-surgeon randomized clinical trial would help to confirm the primary outcome of DETECT-TES and differentiate important secondary outcomes over 2 years. Furthermore, it will be designed to assess longer-term outcomes such as graft survival and rejection in the same cohort with subsequent grant funding.*

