3 OBJECTIVES AND ENDPOINTS

OBJECTIVES	ENDPOINTS	JUSTIFICATION FOR ENDPOINTS
Primary		
Specific Aim 1: To determine whether DMEK has superior post-operative best-spectacle corrected visual acuity (BSCVA) compared to UT-DSAEK and DSO	BSCVA at 12 months	The most clinically important outcome for patients
Specific Aim 2: To determine if rho-kinase inhibitors affect endothelial cell loss in patients undergoing endothelial keratoplasty	Endothelial cell density at 12 months	Endothelial cell loss corresponds with risk of subsequent graft failure
Secondary		
Specific Aim 1: To determine whether DMEK has superior post-operative BSCVA compared to UT-DSAEK and DSO	BSCVA at 3, 6, and 24 months	The most clinically important outcome for patients
Specific Aim 2: To assess the effect of surgery type on endothelial cell loss	Endothelial cell loss at 3, 6, 12, 24 months	Endothelial cell loss corresponds with risk of subsequent graft failure

DETECT

Version 5.0
21 March 2023

OBJECTIVES	ENDPOINTS	JUSTIFICATION FOR ENDPOINTS
Specific Aim 1: To assess the safety profile of each surgery type	Complications over the course of the entire study period, including re-bubble rate, graft rejection, and primary graft failure	Complications rates are important to consider when deciding on a surgery type
Specific Aim 2: To determine if rho-kinase inhibitors affect endothelial cell loss in patients undergoing endothelial keratoplasty	Endothelial cell density at 3, 6, and 24 months	Endothelial cell loss corresponds with risk of subsequent graft failure
To determine the effect of study interventions on quality of life	National Eye Institute Visual Function Questionnaire (VFQ) post-operatively at 3 months and 12 months as compared to baseline	Quality of life is an important patient outcome and will help determine if any differences in BSCVA or endothelial cell density are clinically relevant. The previous DETECT-TES found DMEK to have significantly better visual acuity outcomes but no difference in VFQ
To determine the effect of study interventions on adverse events	Adverse events over entire study period	To ensure safety of the interventions
To assess the relative role of light scatter on visual acuity	Pentacam densitometry at baseline and post-operatively at 3, 6, 12, 24 months	Correlates with clinical outcomes, and may provide a sensitive surrogate endpoint for future clinical trials

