9.4.3 ANALYSIS OF THE SECONDARY ENDPOINTS

We will use the definition of graft failure and displacement previously outlined by the Corneal Preservation Time Study (CPTS).⁵⁰ Graft failure will be defined as the occurrence of one of the following: 1) cornea which requires re-grafting for any reason; 2) cornea which remains cloudy [per the CPTS grading scale of recipient stroma clarity without clearing either if a) cloudy on the first postoperative day which does not clear within 8 weeks, or b) initially clear postoperatively but becomes and remains cloudy for 3 months.

CPTS Graft Failure Classification

- 1) Early: cloudy or equivocal recipient stroma on the first postoperative day that does not clear or requires a re-graft within 8 weeks and is associated with intra- and/or perioperative complications
- 2) Primary Donor: cloudy or equivocal recipient cornea on the first postoperative day that does not clear or requires a re-graft within 8 weeks in the absence of surgical complications*
- 3) Graft rejection: clouded recipient central stroma following an allograft reaction that was initially clear
- 4) Non-rejection: graft that had clear central recipient stroma on the first post-operative visit but becomes cloudy due to causes other than an immune event (e.g. surface failure, infection, glaucoma/hypotony, endothelial decompensation, interface irregularity/opacity, stromal scarring, blunt or penetrating trauma, or other causes
- 5) Refractive/visual: graft that requires re-grafting due to inadequate vision while the recipient central stroma is clear

DETECT

Version 5.0
21 March 2023

* Differs from EBAA Medical Standards which defines primary donor failure as a re-graft that is performed > than 8 weeks after keratoplasty.⁵¹

CPTS Graft displacement Classification

- 1) Donor positioning: recorded as centered, decentered, total dislocation in anterior chamber, total dislocation in posterior chamber
- 2) Partially detached: yes, no
- 3) If partially detached: central, peripheral, both & % of detachment: 0 to less than 25%, 25 to less than 50%, 50 to less than 75%, 75 to 100%

Other Secondary Outcomes.

Within each secondary outcome group, we will correct for multiple comparisons across the two factorial treatments using a Holm-Bonferroni approach to control the family-wise error rate.

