Cost-effectiveness analysis. A supplementary analysis will use individual-level cost outcomes as well as individual-level health outcomes. We propose to report standard cost-effectiveness acceptability curves based on bootstrap resampling at the individual level from both control and intervention subjects (for a statistical, clinical-trial based, cost-effectiveness analysis from a health care system perspective).⁵³ The outcome variable will be cost per line of vision gained.

Treatment allocation survey. We will perform a formal assessment of study participant masking as outlined in SAP 6.4.1

DETECT

Version 5.0
21 March 2023

Adverse Events. All adverse events, including the number of re-bubble procedures, graft failure and graft rejection will be tabulated and reported. Statistical comparisons will be conducted using Fisher's exact test, but with the caution that failure to find evidence of a difference cannot be used to infer a lack of risk difference for rare outcomes such as primary graft failure since the study is not powered to examine these.

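### Aim 1 is worded as superior acuity with similar safety, but the only complication comparison stated is a Fisher test of difference, which cannot show similarity

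*Protocol*

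**What the plan says.** Sections 1.1 and 9.1 set out Aim 1 as finding whether DMEK gives superior BSCVA "compared with UT-DSAEK or DSO with a similar safety profile". Neither section says what would count as similar. The lettered hypotheses under the aim concern visual acuity only.

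The objectives table in Section 3 differs. Its primary row for Aim 1 has no safety clause, and safety appears as a secondary objective: "Specific Aim 1: To assess the safety profile of each surgery type". The matching secondary endpoint in Section 9.1 is "Complications over the course of the entire study period, including re-bubble rate, graft rejection, primary graft failure, and need for further surgery".

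Section 9.4.3 tabulates adverse events, including re-bubbles, graft failure and rejection. It compares them by Fisher's "exact test, but with the caution that failure to find evidence of a difference cannot be used to infer a lack of risk difference", and the sentence goes on "for rare outcomes such as primary graft failure since the study is not powered to examine these". The same section states: "Within each secondary outcome group, we will correct for multiple comparisons across the two factorial treatments using a Holm-Bonferroni approach". Section 9.2 gives no power for any complication.

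**The concern.** A similarity aim needs an analysis that can limit how large an excess of harm the data still allow. Fisher's test asks only whether a difference has been shown. In a small trial a non-significant result is the expected outcome over a wide range of true differences, so it is weak evidence of similarity.

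The protocol sees this for primary graft failure and says so. It does not clearly say it for re-bubbling, rejection or further surgery, while the wording of Aim 1 covers the whole safety profile. A report could therefore state better vision with similar safety when the data still allow a sizeable excess of complications.

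A difference is not far-fetched. Section 2.3.1 says DMEK may carry more tissue loss, repeat air injection and detachment than UT-DSAEK. Section 2.2 reports similar complication rates from the 50-eye pilot trial, then concedes that the pilot was not powered for re-bubbling or primary graft failure. It offers the larger trial to "confirm the primary outcome of DETECT-TES and differentiate important secondary outcomes over 2 years".

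The Holm rule is a side issue. If it reaches complications, it lowers the significance level for a comparison in which a missed difference is the error to fear.

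**Working it through.** **Inputs from the protocol (Section 9.2).** DETECT I: 80 per surgery arm, difference 0.11 logMAR, SD 0.2. DETECT II: 30 per arm, difference 0.13, SD 0.147. Both: two-sided alpha 0.05 and 10% loss, leaving 72 and 27 evaluable per arm.

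**Step 1: the protocol's own power for BSCVA.** Power = Φ(δ / (SD·√(2/n)) − 1.96).
- DETECT I: 0.2 × √(2/72) = 0.0333; 0.11/0.0333 = 3.30; Φ(1.34) = 91.0%.
- DETECT II: 0.147 × √(2/27) = 0.0400; 0.13/0.0400 = 3.25; Φ(1.29) = 90.1%.

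Both agree with the stated figure of at least 90%. The sample sizes suit the acuity endpoint.

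**Step 2: what Fisher's test can see at these sizes.** The protocol gives no planning rates for complications, so every rate here is an assumption. For each pair of true rates, all 2×2 tables were enumerated and the binomial probabilities summed wherever the two-sided Fisher p exceeds 0.05. The result is the chance of missing the difference:

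| Assumed true rates | 80/arm | 72/arm | 30/arm | 27/arm |
|---|---|---|---|---|
| 2% vs 4% | 97% | 98% | 99.9% | about 100% |
| 5% vs 10% | 86% | 88% | 98% | 99% |
| 10% vs 20% | 65% | 68% | 90% | 92% |
| 20% vs 40% | 26% | 30% | 70% | 74% |

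For 80% power from a 10% base, the other arm would need about 29% in DETECT I and 44% in DETECT II, with all randomised eyes evaluable.

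**Step 3: what an interval would show.** With a true rate p in both arms, the 95% half-width of the risk difference is 1.96·√(2p(1−p)/n). At p = 10%:
- n = 80: 1.96 × √(0.18/80) = 1.96 × 0.0474 = 9.3 points (9.8 at n = 72).
- n = 30: 1.96 × √(0.18/30) = 1.96 × 0.0775 = 15.2 points (16.0 at n = 27).

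**Step 4: Holm, if it applies.** In DETECT I the smaller of the two factorial p-values would be tested at 0.025. With 80 per arm, the miss rate for 10% vs 20% rises from 65% to 75%. This is an upper bound: if the smaller p-value belongs to the other factor and is significant, the surgery comparison is tested at 0.05.

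**Step 5: the passages side by side.** Sections 1.1 and 9.1 seek similar safety. Section 3 seeks to assess safety. Section 9.4.3 tests for a difference and, for rare outcomes, rejects the inference that the Aim 1 wording invites. These passages do not agree.

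**The case against.** The strongest reply is that the protocol sets no rule under which p > 0.05 counts as similar. The hypotheses under Aim 1 are about acuity, complications are a secondary endpoint, and no joint success criterion exists. The sentence that names Fisher's test warns that "failure to find evidence of a difference cannot be used to infer a lack of risk difference for rare outcomes". All of this stands. A reader might infer that a non-significant test would automatically establish similarity, or that Aim 1 could formally be declared met on that basis. The documents support neither reading. What remains is that the aim's wording invites the inference and the caution stops short of the commoner complications.

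Further objections also carry weight:
- A margin or an interval may be in the SAP, which is not shown, so their absence is not the finding. The disagreement between Sections 1.1 and 9.1 and Sections 3 and 9.4.3 lies within the protocol itself.
- The size depends on assumed rates. At 20% vs 40%, DETECT I would detect the difference about three times in four.
- The background evidence is mixed. Section 2.2 cites an 18% re-operation rate, but from a DMEK series with no comparator. It also calls re-bubble and primary graft failure rates comparable across two large series.
- That Holm covers safety tests is a reading. The adverse-event paragraph does not mention it, although it falls under the same group of secondary outcomes.
- DSO implants no donor graft, so graft-based events have no direct counterpart in that arm, and 10% vs 20% does not describe them. Under an assumed 0% vs 20%, the miss rate with 30 per arm is 43%. For the same reason, a single graft-based composite judged against a margin would not suit DETECT II and is not proposed here.

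**Conclusion.** The point holds as a conflict between the stated aim and the stated analysis. The protocol words a primary aim as similar safety, names only a test of difference for complications, and limits its own caution to rare outcomes. A non-significant result could be read as similar, although nothing in the protocol says that it must be.

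Under an assumed doubling from 10% to 20%, that result would occur about 65% of the time in DETECT I and 90% in DETECT II with all eyes evaluable, or 68% and 92% after the planned 10% loss. Under 20% versus 40% the figures are 26% and 70% with all eyes evaluable. Even with equal 10% rates, the data would typically leave about ±9 points open in DETECT I and ±15 in DETECT II. All these rates are assumptions. The acuity power calculations are not in question.

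**What to change.** 1. Delete the similar-safety phrase from Aim 1 in Sections 1.1 and 9.1, so that both match Section 3.
2. In Section 9.4.3, report each complication as a risk difference (DMEK minus comparator) with a 95% confidence interval alongside Fisher's test. For DETECT II, use only events that can occur in both arms, such as need for further surgery.
3. Extend the caution in Section 9.4.3 from rare outcomes to all complication comparisons.
4. State that the Holm correction does not apply to adverse-event and complication comparisons.

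These are wording changes in the protocol, carried into the SAP, and need no extra patients or data. The cost is in what may be claimed: neither trial, and DETECT II in particular, could claim similar safety from a non-significant test.

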9.2 SAMPLE SIZE DETERMINATION

DETECT I

We will power the study for each comparison. For both primary analyses, we used a standard sample size formula based on an ANCOVA that conditions on a baseline outcome measure.⁴⁹ Given that endothelial cell density and visual acuity are different, non-correlated outcomes ($R=0.08$ in the DETECT pilot study) with different randomization, each will have its own alpha of 0.05. Specifically, we will be comparing:

- I. With 80 patients per group (160 total), we estimate that we will have at least 90% power to detect a difference in logMAR of 0.11 at 12 months, assuming an outcome SD of 0.2, a 2-sided alpha of 0.05, and 10% loss-to-follow-up. Under the same assumptions but 80% power, the minimum detectable difference in logMAR is 0.09. We assumed a higher SD in the calculation compared with the SD estimated in the DETECT pilot (adj. SD=0.147) to allow for more complex eyes enrolled in the trial.
- II. With 80 patients per group (160 total), we estimate that we will have at least 90% power to detect a 7% difference in ECL between enrollment and 12 months, assuming an outcome SD of 0.134 estimated from the DETECT pilot study, a 2-sided alpha of 0.05, and 10% loss-to-follow-up. If we assume a larger outcome SD for more complex eyes (SD=0.18), we will have at least 90% power to detect a 10% difference in ECL.

DETECT II

With 30 patients per group (60 total), we estimate that we will have at least 90% power to detect a difference in logMAR of 0.13, assuming an outcome SD of 0.147, a 2-sided alpha of 0.05, and 10% loss-to-follow-up. The SD was estimated from the DETECT pilot study and was adjusted for correlation between baseline and 12-month measurements (outcome SD = 0.163, correlation = 0.428, adjusted SD = 0.147). Under the same assumptions but 80% power, the minimum detectable difference is 0.11 logMAR.

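### Three detectable differences in protocol Section 9.2 are rounded down: power for a 7% ECL difference is about 88%, and two 80%-power BSCVA figures give about 77% to 78.5%

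*Protocol*

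**What the plan says.** Section 9.2 sizes each DETECT I comparison with 80 patients per group (160 in total), using an ANCOVA-type formula. The inputs are two-sided alpha 0.05 for each primary outcome and 10% loss to follow-up.

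- **ECL, DETECT I.** The lead claim is "at least 90% power to detect a 7% difference in ECL between enrollment and 12 months, assuming an outcome SD of 0.134", the SD coming from the pilot. The same item then gives a second scenario for this outcome: "If we assume a larger outcome SD for more complex eyes (SD=0.18), we will have at least 90% power to detect a 10% difference in" (the sentence ends by naming that outcome).
- **BSCVA, DETECT I.** The claim is "at least 90% power to detect a difference in logMAR of 0.11 at 12 months, assuming an outcome SD of 0.2". It is followed by "Under the same assumptions but 80% power, the minimum detectable difference in logMAR is 0.09". The protocol explains that 0.2 was chosen above the adjusted pilot SD of 0.147 because more complex eyes would be enrolled.
- **BSCVA, DETECT II.** With 30 per group, SD 0.147 and the same alpha and loss, it gives 0.13 logMAR at 90% power. At 80% power, "the minimum detectable difference is 0.11 logMAR".

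No correlation between baseline and 12-month values is given for ECL. For BSCVA in DETECT II, Section 9.2 gives one (0.428) and shows how it turns 0.163 into 0.147.

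**The concern.** The ECL claim is worded as a floor on power, and the two 80%-power figures are presented as the smallest differences detectable at that power. Such statements stay true if the difference is rounded up and become false if it is rounded down. When the stated inputs are put through the standard formula, three of the figures come out on the wrong side.

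All three belong to primary endpoints, and Section 9.4.2 refers back to the detectable effects of Section 9.2 when it discusses power for the drug-by-surgery interaction. At stake is the accuracy of the stated design properties. The analysis and the number of patients are not affected.

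A related gap is the choice of SD. For BSCVA the raised, complex-eye SD is the base case. For ECL in the same 160 patients the unraised pilot SD comes first and 0.18 follows as an alternative. The protocol does not say which ECL value the trial is planned on.

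**Working it through.** **Inputs (all from Section 9.2).** DETECT I: 80 per group, so 80 × 0.9 = 72 evaluable. DETECT II: 30 per group, so 30 × 0.9 = 27 evaluable. Two-sided alpha 0.05 (z = 1.960). SDs: 0.134 and 0.18 (ECL), 0.2 (BSCVA, DETECT I), 0.147 (BSCVA, DETECT II).

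**Formulas (normal approximation, 1:1).**
- SE = SD × √(2/n)
- Power = Φ(difference/SE − 1.960)
- Detectable difference = SE × (1.960 + z for power). The bracket is 3.2415 for 90% and 2.8016 for 80%.

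**Step 1: reproduce the protocol's figures.** Each SD is entered as printed.

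| Quantity | Exact | Printed | Direction |
|---|---|---|---|
| BSCVA, DETECT I, 90% | 0.1081 | 0.11 | up |
| BSCVA, DETECT I, 80% | 0.0934 | 0.09 | down |
| ECL, SD 0.134, 90% | 0.0724 | 7% | down |
| ECL, SD 0.18, 90% | 0.0972 | 10% | up |
| BSCVA, DETECT II, 90% | 0.1297 | 0.13 | up |
| BSCVA, DETECT II, 80% | 0.1121 | 0.11 | down |

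All six printed figures equal the exact value rounded to two decimals. This supports the reading that 72 (or 27) per group was used and that the printed SDs went straight into the formula. The adjusted SD for DETECT II also reproduces: 0.163 × √(1 − 0.428²) = 0.147.

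**Step 2: power at the three figures rounded down.**
- ECL 7%, SD 0.134: SE = 0.134 × √(2/72) = 0.02233; 0.07/0.02233 = 3.134; power = Φ(1.174) = 88.0% (87.6% with the noncentral t).
- BSCVA 0.09, SD 0.2: SE = 0.2 × √(2/72) = 0.03333; 0.09/0.03333 = 2.70; power = Φ(0.740) = 77.0% (76.5% with t).
- DETECT II 0.11, SD 0.147: SE = 0.147 × √(2/27) = 0.04001; 0.11/0.04001 = 2.749; power = Φ(0.789) = 78.5% (77.0% with t). The exact 80% difference is 0.1121 by the normal formula and 0.1142 by t.

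**Step 3: figures rounded up.** On the normal formula, 10% ECL at SD 0.18 gives 91.5%, 0.11 logMAR at SD 0.2 gives 91.0%, and 0.13 logMAR in DETECT II gives 90.1%. The first two also hold with t (91.2% and 90.6%). The third drops to 89.0% with t, too close to press.

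**Step 4: what would rescue the ECL claim.**
- Leaving out the 10% loss (80 evaluable per group) gives 91.1%, but the sentence says the loss is included.
- If 0.134 is an SD before baseline adjustment, 90% at 7% needs an adjusted SD of 0.07/(3.2415 × √(2/72)) = 0.1296. The correlation required is √(1 − (0.1296/0.134)²), about 0.26.

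**Step 5: proposed replacements.** ECL 7.3% at SD 0.134: 0.073/0.02233 = 3.269, power 90.5%. BSCVA 0.094 at SD 0.2: 2.82, power 80.5%. DETECT II 0.115: 2.874, power 82.0% (80.5% with t).

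**The case against.** The strongest reply is that this is ordinary two-decimal rounding. That stands as an explanation: three of the six figures round up and three round down, so a reader who infers a systematic tilt towards favourable figures would be wrong. It does not make the three sentences true, because a floor on power fails as soon as the difference falls below the exact value.

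The second reply concerns the SD. The formula is said to condition on baseline, and 0.134 is labelled only as an outcome SD, a label Section 9.2 also gives to the unadjusted 0.163. If 0.134 is unadjusted, a modest correlation of about 0.26 restores 90% with the 10% loss kept. So one cannot say that the claim holds only by ignoring dropout. Against this, 0.2 and 0.147 carry the same label and reproduce only when entered directly, and no ECL correlation is given. Entering 0.134 directly is therefore the better reading, though not a certain one.

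Third, a reader might compute power for 7% at SD 0.18, find 64.6%, and call the ECL comparison badly underpowered. The documents do not support calling that an error. The protocol never claims 90% for 7% at that SD, and the next sentence states, correctly, that the difference is then 10%. What remains is only that the planning SD is not named.

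Fourth, a reader might add weight by noting that 7% is close to the gap in ECL between the two surgeries in the pilot. The primary ECL test is ripasudil against placebo (Section 9.4.2), and ECL by surgery is a key secondary outcome (Section 9.4.3), so that gap is not the effect the primary test targets.

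**Conclusion.** The point holds as a minor correction. On the protocol's own inputs, with 72 evaluable per group and 0.134 entered directly, power for a 7% ECL difference is about 88%, and 90% is reached at 7.24%. The 80%-power BSCVA differences are 0.0934 logMAR in DETECT I and 0.112 to 0.114 in DETECT II. The printed 0.09 and 0.11 give about 77% and 77% to 78.5%. The gaps are 0.24 percentage points of ECL, about 0.003 logMAR, and 0.002 to 0.004 logMAR.

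The ECL part depends on reading 0.134 as the SD used in the formula. The two BSCVA parts do not, since their SDs are confirmed by the reproduced figures. The 10% ECL difference at SD 0.18 and the 0.11 logMAR at 90% power are correct. Nothing here shows that the trial is too small or that any analysis must change.

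**What to change.** In Section 9.2:

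1. ECL at SD 0.134: state 90% power for a 7.3% difference, or keep 7% and state 88% power. If 0.134 is not yet adjusted for baseline, say so and give the correlation used.
2. BSCVA at 80% power: state 0.094 logMAR for DETECT I and 0.115 logMAR for DETECT II.
3. Leave the 10% ECL difference at SD 0.18 and the 0.11 logMAR at 90% power as they are.
4. Say which ECL SD, 0.134 or 0.18, is the planning value, and why, given that BSCVA in the same patients is planned on an SD raised for complex eyes.

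The cost is a few words and slightly less favourable figures. No patients are added.
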